8.2 Medically-Attended Events and Significant New Medical Conditions

These classes of events will be collected at all study visits, and if offered spontaneously by the subject at any time.

Medically-attended events (MAEs) are adverse events which result in an unscheduled visit to a healthcare provider due to symptomatic illness or injury. These may include office visits, clinic visits, home consultations, or emergency room evaluations for non-life-threatening events that do not result in hospitalization (life-threatening events or hospitalizations are SAEs, see Section 8.3).

Significant new medical conditions (SNMCs) are adverse events that are new (that is, not present at baseline), clinically significant (meaning that they imply an important change in the subject's long-term health status), and typically chronic (requiring an ongoing change in the subject's medical management). This category is not meant to include minor or transient diagnoses or age-related changes.

The eCRF will provide a field in which the investigator may designate AEs as MAEs, SNMCs, or both. Because of the significance of the designation for the subject's health, long-term medical management, and for evaluation of vaccine safety, SNMCs are expected to be substantiated diagnoses, not isolated symptoms which might or might not be a SNMC, and the investigator should record sufficient data in the eCRF to support the diagnosis.

Full details of MAEs and SNMCs (ie, nature, date of onset, and recovery (if applicable) as well as an assessment of severity, relationship to trial agent, seriousness, treatment, and outcome)

will be recorded in the source documentation and captured in the eCRF, and will require the investigator(s) causality assessment.

MAEs and SNMCs will be recorded and summarized from Day 0 to Day 28 for the unblinded data review and from Day 0 to Day 364 following study completion for the final analysis, for all subjects in the Safety Population. Note that MAEs and SNMCs are also included in the overall summary of AEs.

8.3 Serious Adverse Events

A SAE is defined as an AE that results in any of the following outcomes:

- Death,
- An immediate threat to life,
- In-patient hospitalization or prolongation of an existing hospitalization. (Hospitalization is defined as an actual admission, not a 24-hour stay or emergency room visit; note that elective surgeries, undertaken for conditions present prior to receipt of trial drug and without complication, should not be considered SAEs),
- A persistent or significant disability/incapacity (substantial disruption of an ability to conduct normal life functions), or
- A congenital anomaly or birth defect (not relevant to this protocol).

The eCRF will provide a field for designating an AE as SAE. SAEs are associated with enhanced reporting requirements (see Protocol, Section 8.3).

A listing of subjects with SAEs will be summarized from Day 0 to Day 28 for the unblinded analysis, and from Day 0 to Day 364 following study completion for the final analysis, for all subjects in the Safety Population.

8.4 Vital Signs

Descriptive statistics for vital signs (blood pressure, heart rate, oral temperature, respiratory rate) at Days 0, 7, 28, and 182 will be presented by treatment group for all subjects in the Safety Population.

9 SAMPLE SIZE CONSIDERATIONS

This study has a single comparison between Quad-NIV and Fluzone Quadrivalent at Day 28 post-vaccination for the primary immunogenicity objective. No adjustment of the Type I error rate for multiple comparisons is warranted since the simultaneous successes of all 8 comparisons planned for the 4 strains contained in the vaccines and the two endpoints (GMT and SCR) are required for the demonstration of the primary non-inferiority objective of the study.

Non-inferiority is defined as the lower bound of the 2-sided 95% CI on the ratio of GMTs (Quad-NIV vs Fluzone) ≥ 0.67 (ie, unadjusted 1-sided p-value < 0.025 against the null hypothesis of H0: Ratio of GMT < 0.67) and the lower bound of the two-sided 95% CI on the

difference of the SCRs (Quad-NIV - Fluzone) \geq -10% (ie, unadjusted 1-sided p-value < 0.025 against the null hypothesis of H0: Difference of SCRs < -10%).

For the calculation of sample size estimation, we used assumptions of true differences, ie, the ratio of GMTs (Quad-NIV vs Fluzone Quadrivalent) is 1.0 for all 4 homologous strains, and the difference of the SCRs is -2% for each of the 4 homologous strains, based on the average performance in the previous trial (qNIV-E-201). To achieve an overall 90% power (ie, ~ 97.5% power for each of the 4 strains) to demonstrate a non-inferiority margin for SCR difference of -10%, the SCR of reference group (Fluzone Quadrivalent) is assumed to be 0.5 and the SCR of treatment group (Quad-NIV) is assumed to be 0.48 under the null hypothesis of inferiority (H0: Difference of SCRs < -10%). The significance level of the testing is 0.025. Sample size was estimated to be 1195 in each group by assuming equal size in each group. The sample size accounted for a 10% attrition rate for the per-protocol population such that the primary analysis population for all immunogenicity endpoints will be 1325 in each group.

In a previous trial (qNIV-E-201), the observed vaccine-homologous strain-specific standard deviations of \log_{10} HAI titers ranged from approximately 0.3 (B/Colorado/06/2017 and B/Phuket/3073/2013) to approximately 0.4 (A/Singapore/INFIMH-16-0019/2016 and A/Michigan/45/2015). The calculated power for each strain, unadjusted for multiple comparisons, is close to 100% to detect a 1.5-fold difference in GMTs. For 4 strains, this study is designed to exclude a GMT ratio of < 0.67 with 100% power. Therefore, for demonstrating non-inferiority for 4 strains with the true ratio of GMTs of 1.0 and the true SCR differences of -2%, this study provides \geq 90% overall power.

For safety endpoints, the probability of observing at least 1 adverse event among 1325 subjects for Quad-NIV is > 90% if the true rate of such events is 0.18%. With 1325 subjects for Quad-NIV, observing no adverse events of interest (eg, vaccine-related SAE) would represent an upper bound of the 1-sided 95% CI on the percentage of such event is 0.2%.

10 PRELIMINARY UNBLINDED AND FINAL ANALYSES

An unblinded analysis will be conducted upon completion of all Day 28 visits, which will include all primary endpoints (HAI antibody responses assayed with egg-propagated virus) testing of associated Day 28 serum samples for all 4 vaccine homologous influenza strains (ie, 2 influenza A and 2 influenza B strains) and safety data through Day 28. Data concerning secondary and exploratory endpoints will be included in the unblinded review of Days 0 and 28 as they become available. For the review, treatment codes will only be unblinded after the data are deemed ready for the analysis after all subjects have completed the Day 28 visit and the data are monitored.

In order to execute Day 28 unblinded data review, a select group of trial staff will be unblinded at the CRO and at Novavax. All personnel unblinded to the trial data will be documented. No individual unblinded at a subject treatment level will be involved in follow-up safety monitoring. Specifically, personnel at the clinical study site including, investigators and study staff, research site, immunology laboratory, and study subjects will remain blinded to treatment assignments until the end of study (ie, Day 364).

Day 364 final analysis will be conducted when all immunogenicity and safety data through Day 364 have been entered, reviewed, and all queries related to the data have been addressed. Immunogenicity data required prior to the Day 364 analysis will include the mandated timepoints (Days 0 and 28) for the primary and secondary endpoints, with the latter including the four vaccine-homologous A and B strain(s) and at least one antigenically-drifted influenza strains for HAI antibody titers assayed with both egg-propagated virus and wild-type VLP reagents. Immunogenicity data required prior to the Day 364 analysis will also include HAI antibody response at additional time-point Day 182 tested with a subset of subjects pursuant to secondary endpoints. Testing of additional antigenically-drifted influenza strain responses by HAI, and also Microneutralization (MN) and cellular response testing pursuant to the exploratory objectives may be completed later and included in addenda to the study report.

Immunogenicity and safety analyses from the Day 28 unblinded analysis may be presented in an abbreviated Unblinded clinical study report (CSR) drafted by the Sponsor that may be submitted to regulatory authorities as needed.

The final CSR will present the balance of all safety and immunogenicity (if any) data through Day 364 (the scheduled end of trial). The database will be locked and the final CSR prepared, when all of the above data have been entered, reviewed, and all queries related to the data have been addressed. Any decisions to deviate from the planned analyses will be described in detail in the final CSR.

Any decisions to deviate from the planned analyses stated in the SAP will be described in detail in the final study report.

11 COMPUTER METHODS

Statistical analyses will be performed using SAS® version 9.4 or higher in a Windows environment.

Sample size calculations based on two-sample t-test were performed using PASS 14, version 14.0.15 released on May 23, 2019.

12 DATA HANDLING CONVENTIONS

All output will be incorporated into Microsoft Word or Excel files, or Adobe Acrobat PDF files, sorted and labeled according to the International Conference on Harmonisation (ICH) recommendations, and formatted to the appropriate page size(s).

All statistical analyses will be 2-tailed and assessed at the 5% significance level. For all analyses, p-value of < 0.05 will be considered statistically significant.

Tabulations will be produced for appropriate demographic, baseline, and safety parameters. For categorical variables, summary tabulations of the number and percentage of subjects within each category (with a category for missing data) of the parameter will be presented. For continuous variables, the number of subjects, mean and standard deviation (SD), median, minimum, and maximum values will be presented.

All references to analysis of GMT will be interpreted as analysis of the log_{10} of titer values or of the reciprocal titers (eg, the reciprocal titer of 1:160 is the number 160) or of concentrations.

The individual immunogenicity titer values recorded as below the LLOQ of the assay will be set to half LLOQ for the purposes of GMT and GMR analyses. The LLOQ values will be provided by corresponding lab or CRO as part of the data transfer.

Medical history and AEs will be coded using MedDRA Version 22.0.

Each parameter will be reported with the below defined decimal numbers in Table 6.

Table 6: Decimal Numbers for Parameters

Parameter	Number of Decimal			
Number of subjects (e.g. N, N1, N2)	0			
Percentage (%)	1			
Mean	1 more decimal than raw data			
Standard Deviation (SD)	1 more decimal than mean			
Median, Min, Max	as same decimal as raw data			
GMT, GMR _{Post/Pre} , their corresponding 95% CIs	1			
Ratio of GMTs, its corresponding 95% CIs	2			
SPR (%), SCR (%), SPR difference, SCR difference, their corresponding 95% CIs	1			
P value for GMR _{Post/Pre} and Ratio of GMTs	3			

Note: For analysis of exploratory CMI response, up to 5 decimal numbers will be presented depending on number of significant digits for each parameter.

12.1 Baseline Definitions

For all analyses, baseline will be defined as the last non-missing measurement prior to the first administration of the study material. For immunogenicity analysis, baseline will be the sample drawn prior to the first vaccination, on the day of vaccination.

12.2 Adjustments for Covariates

Comparison of GMTs between treatment groups will be adjusted for pre-vaccination titer.

12.3 Multiple Comparisons/Multiplicity

No multiplicity adjustment will be applied for the secondary endpoints.

12.4 Withdrawals, Dropouts, and Loss to Follow-up

The Investigator may withdraw any subject from the study at any time for medical reasons or if the subject is unable or unwilling to comply with the protocol. A subject may elect to discontinue his/her participation and withdraw from the study at any time. A subject withdrawing from the study may do so without detriment to access to medical care. See Sections 6.4 - 6.5 of the protocol for more details on withdrawal of subjects.

Any subject discontinuing from the trial at any time other than the screening period will not be replaced. A subject who receives the investigational product but withdraws for any reason will be encouraged to return for the safety assessments according to the Schedule of Procedures (Appendix 1). If the subject does not wish to remain in the study, the subject can choose to withdraw consent and discontinue at any time as outlined in Section 6.5 of the protocol.

12.5 Missing, Unused, and Spurious Data

In general, there will be no substitutions made to accommodate missing data points. All data recorded on the eCRF will be included in data listings that will accompany the CSR.

When tabulating AE, Concomitant Medications, and Hospitalizations data, partial dates of event onset will be handled as follows:

- If the day of the month is missing, the onset date will be assumed to be the date of the Day 0 vaccination or first of the month, whichever is later, in order to conservatively report the event as vaccine-emergent.
- If the month or year (or both) of the onset date is missing, impute month or year (or both) which makes the imputed date most adjacent to the first dosing date.
- If the onset day and month are both missing, the event onset will be coded to the date of the Day 0 vaccination or 1st January of the year, whichever is later, in order to conservatively report the event as vaccine-emergent.
- A completely missing onset date will be coded as the date of the Day 0 vaccination, unless the end date suggests it could have started prior to this in which case impute the 1st January of the same year as the end date.
- When imputing a start date ensure that the new imputed date is prior to the end date of the AE or med.

A conservative approach will be taken to assess the relationship of an event to test article: if the relationship of an event is missing, it will be considered treatment-related. Missing severity for an AE will not be imputed.

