6.2 Concomitant Medication

The assessment of concomitant medication use by the subject during the study will coincide with the collection period of adverse events. Concomitant medications recorded on the Concomitant Medications CRF will be summarized by WHO-DRUG Anatomical Therapeutic Chemical (ATC) Term and standardized (generic) medication name based on WHODD GLOBAL B3-Mar2019. The number (percentage) of subjects who record one or more concomitant medications will be presented by treatment group for all subjects in the Safety Population. Multiple occurrences of medication usage for a subject will be counted only once within an ATC term and standardized medication name. The presentation of concomitant medications will include all medications recorded on the Concomitant Medications CRF, including medications with a missing or partial start date or a start date prior to Study Day 0 vaccination. A separate listing of treatment-emergent new concomitant medications will be presented.

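### SAP 12.5 dates a medication still in use after vaccination to Day 0 even when its recorded start month or year is earlier, so the SAP 6.2 listing could show prior therapy as new

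*SAP*

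**What the plan says.** SAP 12.5 introduces five bullets with "When tabulating AE, Concomitant Medications, and Hospitalizations data, partial dates of event onset will be handled as follows". In order, they say:

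1. Day missing: "the onset date will be assumed to be the date of the Day 0 vaccination or first of the month, whichever is later", with the stated aim "in order to conservatively report the event as vaccine-emergent".
2. Month or year missing, or both: "impute month or year (or both) which makes the imputed date most adjacent to the first dosing date".
3. Day and month both missing: "the event onset will be coded to the date of the Day 0 vaccination or 1st January of the year, whichever is later", with the same stated aim.
4. Start date completely missing: Day 0, unless the end date points to an earlier start, in which case 1 January of the end-date year.
5. A check on all of these: "When imputing a start date ensure that the new imputed date is prior to the end date of the AE or med".

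The same section says that data points are in general not substituted, and that everything entered on the eCRF goes into the listings supplied with the CSR.

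SAP 6.2 describes two medication outputs. The main table counts every drug on the medication form, "including medications with a missing or partial start date or a start date prior to Study Day 0 vaccination". Then: "A separate listing of treatment-emergent new concomitant medications will be presented". SAP 6.2 neither defines a new medication nor says which date selects the listing.

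**The concern.** Bullets 1 and 3 are designed for events whose timing relative to vaccination is uncertain. Calling such an event vaccine-emergent is a cautious choice for safety. A drug recorded as started in March 2015 carries no such uncertainty: whatever the day, it began before vaccination. The rule replaces that recorded fact with Day 0.

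Such records are plausible. Protocol 5.1 admits subjects with chronic diagnoses, Protocol 6.1.1 takes a medication history covering the past year, and SAP 6.2 itself expects partial start dates and starts before Day 0.

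The rule is also uneven. Bullet 4 can place a completely missing start before vaccination when the end date suggests it, while bullet 1 cannot do so for a drug in continuing use whose earlier month is on record.

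At stake is the one listing meant to separate new drugs from existing ones. If it is selected on imputed dates, known prior therapy would appear as started on vaccination day.

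**Working it through.** The plan gives no figure to reproduce; this is a check of logic. The documents give no vaccination dates, so Day 0 (D0) is assumed: 15 Oct 2019 for worked examples, and a range of dates for the sweeps.

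**Step 1: what bullets 1 and 3 return.**
- Bullet 1: start = max(D0, first of recorded month).
- Bullet 3: start = max(D0, 1 January of recorded year).

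If the recorded month or year is before that of D0, the second term is always before D0, so the result is D0. A start of March 2015 gives max(15 Oct 2019, 1 Mar 2015) = 15 Oct 2019. A start of 2015 alone gives max(15 Oct 2019, 1 Jan 2015) = 15 Oct 2019.

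**Step 2: whether the end-date check (bullet 5) prevents it.** Recorded start months from January 1990 to September 2019 number 29 × 12 + 9 = 357. Recorded years 1990 to 2018 number 29.

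| Medication end date | Months dated to D0 and passing bullet 5 | Years dated to D0 and passing bullet 5 |
|---|---|---|
| Ongoing | 357 of 357 | 29 of 29 |
| 16 Oct 2019 | 357 of 357 | 29 of 29 |
| 20 Nov 2019 | 357 of 357 | 29 of 29 |
| 15 Oct 2019 (D0) | 0 of 357 | 0 of 29 |
| 1 Sep 2019 | 0 of 357 | 0 of 29 |

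The check therefore works only for drugs that ended on or before Day 0. Repeating Step 1 for every D0 from 1 Sep to 29 Dec 2019 gave no exceptions.

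**Step 3: how far the date moves.** With D0 = 15 Oct 2019, a true start in October 2018 moves by 349 to 379 days and one in September 2019 by 15 to 44 days. Over the 12 preceding calendar months the range is 15 to 379 days.

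**Step 4: bullets 2 and 3 on year-only dates.** Both apply and no precedence is stated. If bullet 2 supplies only the month and bullet 1 the day, the result equals bullet 3 for 11 of 11 recorded years (2010 to 2020). If bullet 2 supplies the nearest date itself, 2015 becomes 31 Dec 2015 rather than 15 Oct 2019; the two bullets then agree for 2019 and 2020 and differ for the other 9 of 11 years.

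**Step 5: which outputs use the start date.** The main table in SAP 6.2 takes all drugs whatever their start, so imputation cannot change it. The new-medication listing is the only medication output described for which a start date could decide inclusion.

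**Step 6: behaviour of the change proposed below.** Take each D0 from 1 Sep to 30 Nov 2019 (91 dates) and the 12 calendar months before its month: 91 × 12 = 1092 cases. The current rule gives D0 in 1092 of 1092. Using the first of the recorded month gives a date on or after D0 in 0 of 1092. With D0 = 15 Oct 2019, recorded months October, November and December 2019, January 2020 and June 2020, and recorded years 2019 and 2020, give the same date under both rules. A start of September with no year stays as now: bullet 2 supplies 2019, then max(15 Oct 2019, 1 Sep 2019) = 15 Oct 2019.

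These counts hold by construction. They describe the rule, not its impact.

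**The case against.** The strongest reply is that no described medication output need change. The bullets are framed for tabulation, the only medication tabulation in SAP 6.2 ignores start date, and the output in question is a listing. Because SAP 12.5 puts all eCRF entries in listings, the recorded partial date should still be visible, and a reader could see that a drug began earlier. Protocol 6.3 speaks of new or changed medications as something recorded through Day 28, and Protocol 6.1.1 takes the history separately, so newness might be judged without any imputed date. The SAP also chose its direction deliberately, and the worst result is over-inclusion in one descriptive listing.

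Much of this stands and limits the size of the point. It does not remove it. Bullet 5 names medications, so they are plainly in scope. Protocol 8.1 defines treatment-emergent for adverse events by the date and time of administration, which makes a date-based reading of the same term for medications natural. SAP 12.5 is the only partial-date rule described. The stated caution concerns events of uncertain timing, not a drug already known to precede vaccination.

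A reader might infer more: that the main medication table, the per-protocol population or the primary non-inferiority result is distorted. The documents do not support that. The table takes all drugs. Per-protocol exclusions come from a joint assessment by the medical and operational leads before unblinding (SAP 3.4.1.1), with no mention of imputed dates. The primary immunogenicity formulas use no medication date. Nor do the documents show that the listing will misclassify drugs, because its selection rule is not stated.

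**Conclusion.** Wrong as written, but minor. For a drug that is ongoing or stopped after Day 0, bullets 1 and 3 override a recorded pre-vaccination month or year in every case, and the end-date check does not help. This follows from the wording and does not depend on the assumed vaccination dates; only the day counts in Step 3 do.

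The consequence is conditional. Known prior therapy would be listed as new only if the SAP 6.2 listing is selected on imputed start dates. The number of affected records cannot be estimated, because the documents do not say how many start dates are partial. The overlap of bullets 2 and 3 is a smaller ambiguity, worth settling in the same edit.

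**What to change.** For concomitant medications only:

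- **Bullets 1 and 3.** When the year is recorded and the recorded month and year (or the year alone) are before those of Day 0, impute the first of the recorded month (or 1 January of the recorded year) and classify the drug as pre-vaccination. Otherwise keep the present Day 0-or-later default.
- **Precedence.** State that bullet 3 overrides bullet 2 for year-only dates. When the year is missing, bullets 2 and 4 apply as now, and a year supplied by bullet 2 does not count as recorded. Bullet 2 continues to cover a missing month with a known day.
- **SAP 6.2.** State that the treatment-emergent new listing is selected on the start date after this rule.

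The adverse-event rule stays unchanged. The cost is two or three SAP sentences and a small programming change, with no effect on data collection.

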8 TRIAL ASSESSMENT OF SAFETY

8.1 Adverse Events

Adverse events (AEs) are defined as any unfavorable or unintended change in the physical, psychological, or biochemical condition of the subject. An AE temporally related to participation in the trial or due to a procedure performed in the trial, will be documented whether or not considered related to the test article. This definition includes intercurrent illnesses and injuries, and exacerbations of pre-existing conditions. Stable pre-existing conditions which do not change in nature or severity during the trial are not considered AEs; however, these should be collected as part of the medical history. AEs will be considered treatment emergent from the date and time of the first administration of the investigational product.

Data concerning all classes of adverse events will be collected at scheduled visits from the time informed consent is obtained on Day 0 through Day 28, inclusive. After these specified days, data concerning MAEs, SNMCs, and SAEs will be collected (see Sections 8.1.4 and 8.2 for details of these AEs), as well as additional information regarding outcomes/resolutions of AEs reported prior that had no stop date recorded. In addition to the scheduled visits, subjects will be instructed to notify the investigator and/or return to the clinic if any severe AE (solicited or otherwise) or event fulfilling the definition of an SAE occurs at any time following vaccination. If at a scheduled or unscheduled visit, symptoms are presented that would require a physical exam to adequately assess potential AEs, the exam should be performed and vital signs collected. Adverse events will be recorded as observed by the investigator, designated personnel, or as provided by the subject on the diary card or during the in-person visit. Full details of the AE (ie, nature, date of onset, and recovery, as well as an assessment of severity, relationship to trial treatment [unsolicited events only], seriousness, treatment, and outcome) will be recorded in the source documentation and captured in the eCRF, and will generally require the investigator(s) causality assessment, except as discussed below.

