8.1.2 Unsolicited Adverse Events

Unsolicited adverse events are defined as any adverse events occurring within the 7-day window following vaccination and not specifically solicited in the diary, or any adverse event that occurs outside the 7-day diary solicitation period. The number (percentage) of subjects with unsolicited AEs will be summarized by Medical Dictionary for Regulatory Activities (MedDRA) coded by system organ class (SOC) and preferred term (PT). All unsolicited AEs will be assessed for severity (Section 8.4 in Protocol) and for causality (Section 8.5 in Protocol).

The following summaries of unsolicited AEs will be presented for all subjects in the Safety Population as part of the primary analysis of safety:

- Overall summary of unsolicited AEs by treatment group (Days 0 28).
- A summary by severity (normal, mild, moderate, or severe), MedDRA SOC, PT, and treatment group (Days 0 28).
- A summary by relationship (causality) to test article of an AE (unlikely/unrelated, possibly, probably, or definitely) to test article, MedDRA SOC, PT, and treatment group (Days 0 28).

- A summary of severe and related (unlikely/unrelated, possibly, probably, or definitely) AEs, MedDRA SOC, PT, and treatment group (Days 0 28).
- A summary of any AEs including MAEs, SNMCs and SAEs, by MedDRA SOC, PT, and treatment group (Days 0 28).

The final analysis will include the following summaries of unsolicited AEs.

- Overall summary of unsolicited AEs by treatment group (Days 0 364).
- A summary by severity (normal, mild, moderate, or severe), MedDRA SOC, PT, and treatment group (Days 0 364).
- A summary by relationship (causality) to test article of an AE (unlikely/unrelated, possibly, probably, or definitely) to test article, MedDRA SOC, PT, and treatment group (Days 0 364).
- A summary of severe and related (unlikely/unrelated, possibly, probably, or definitely) AEs, MedDRA SOC, PT, and treatment group (Days 0 364).
- A summary of any AEs including MAEs, SNMCs and SAEs, by MedDRA SOC, PT, and treatment group (Days 0 364).

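### SAP 12.5: the rule for a missing onset month or year has no floor at Day 0, so some post-vaccination adverse events can be dated before vaccination

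*SAP*

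**What the plan says.** SAP 12.5 gives five bullets for partial onset dates of AEs, concomitant medications and hospitalizations.

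- **Bullet 1, day missing:** "the onset date will be assumed to be the date of the Day 0 vaccination or first of the month, whichever is later".
- **Bullet 2, month or year missing:** "impute month or year (or both) which makes the imputed date most adjacent to the first dosing date".
- **Bullet 3, day and month missing:** "the event onset will be coded to the date of the Day 0 vaccination or 1st January of the year, whichever is later".
- **Bullet 4, whole date missing:** Day 0, unless the end date suggests an earlier start; then 1 January of the end-date year.
- **Bullet 5, check on every imputed start:** "When imputing a start date ensure that the new imputed date is prior to the end date of the AE or med".

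Bullets 1 and 3 both give their purpose as counting the event, conservatively, as following vaccination. Bullet 2 gives no purpose. Protocol 8.1 collects all classes of AE "from the time informed consent is obtained on Day 0 through Day 28, inclusive", and MAEs, SNMCs and SAEs after that. It also states: "AEs will be considered treatment emergent from the date and time of the first administration of the investigational product". The unsolicited AE summaries (SAP 8.1.2), the MAE and SNMC summaries (8.2) and the SAE listing (8.3) are bounded by Days 0-28 for the unblinded review and Days 0-364 for the final analysis.

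**The concern.** Bullet 2 picks the nearest date on either side of dosing. Its neighbours never go below Day 0 when the recorded parts allow a date on or after it. Bullet 5 sets only an upper limit. Nothing in 12.5 therefore stops bullet 2 from giving a pre-vaccination date to an event that began after vaccination. Such a date is also implausible on its face, because AE collection begins at consent on Day 0.

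The percentages of subjects with AEs, MAEs, SAEs and SNMCs are a primary endpoint (SAP 2.2.1). A negative study day puts the event outside every window used to report them. After Day 28, events are gathered at Days 90, 182 and 364, so the recall intervals are 62, 92 and 182 days. Incomplete dates are most likely there.

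**Working it through.** The plan states no figure for this rule, so there is none to reproduce. The check applies bullet 2 literally.

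**Inputs.** The rules come from SAP 12.5 and the windows from SAP 8.1.2 to 8.3. The documents give no enrolment dates, so Day 0 in autumn 2019 is an assumption. Further assumptions: the day of the month is recorded, each true onset day counts equally, no end date restricts the choice, and ties go to the post-dose date (which favours the plan).

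**Formula.** Let C be all calendar dates that fit the recorded parts. Bullet 2 takes the date c in C that minimises |c − Day 0|.

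**Month missing, year 2019 recorded, Day 0 = 21 October 2019.** The choice depends on the recorded day d:

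- d = 21 to 31: d October is Day 0 to 10 and is chosen.
- d = 1 to 5: d November is Day 11 to 15 and d October is Day −20 to −16. November is chosen.
- d = 6 to 20: d October is Day −15 to −1 and d November is Day 16 to 30. October is chosen, before vaccination.

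The true onsets then fall out as follows:

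- Days 0-28 (21 October to 18 November, 29 days): 6 to 18 November are dated before Day 0, 13/29 = 45%. For example, 14 November (Day 24) becomes 14 October (Day −7), while 28 October (Day 7) is kept.
- Later in 2019 (19 November to 31 December, 43 days): 19-20 November and 6-20 December go before Day 0, 2 + 15 = 17. The other 10 + 5 + 11 = 26 are pulled into Days 0-28, 26/43 = 60%. For example, 25 December (Day 65) becomes 25 October (Day 4).
- Onsets in 2020: the recorded year keeps every candidate after Day 0, so none is lost.
- Days 0-364: (13 + 17)/365 = 8% are dated before Day 0.

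**Year missing, day and month recorded.** For an onset on Day t after 29 February 2020, the same date a year earlier is Day t − 366. It is nearer when 366 − t < t, that is t > 183. Day 183 is an exact tie. Days 184 to 364 are all dated before Day 0: 364 − 184 + 1 = 181 days, 181/365 = 50%. None of Days 0-28 is affected. For example, 20 May 2020 (Day 212) becomes 20 May 2019 (Day −154).

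**Averaged over two assumed dosing periods in 2019:**

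| Missing part and true onset | 15 Sep-15 Nov (62 dates) | 1 Oct-29 Nov (60 dates) |
|---|---|---|
| Month; Days 0-28, dated before Day 0 | 793/1798 = 44% | 767/1740 = 44% |
| Month; Days 0-364, dated before Day 0 | 2039/22630 = 9% | 1545/21900 = 7% |
| Month; after Day 28 but in 2019, pulled into Days 0-28 | 1757/3007 = 58% | 1228/2010 = 61% |
| Year; Days 0-28, dated before Day 0 | 0% | 0% |
| Year; Days 0-364, dated before Day 0 | 11222/22630 = 50% | 10860/21900 = 50% |

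With a floor at Day 0, every share dated before Day 0 becomes 0%.

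**Bullet 5 against bullet 1.** Take an event with a missing start day that ended on Day 0, the recorded month being that of Day 0. Bullet 1 gives Day 0. Bullet 5 requires a start strictly earlier than the end, which is also Day 0. No date satisfies both, and the SAP names no fallback.

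**The case against.** The strongest reply is that this will hardly ever matter.

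- Bullet 2 bites mainly when the day is recorded but the month or year is not, which is an odd pattern.
- Onset date is a required AE detail (Protocol 8.1), and analysis waits for queries to be resolved (Protocol 9.2).
- All eCRF data go into listings and SAEs get narratives, so a misdated record stays visible.
- The safety analysis is descriptive, with no test or decision rule attached.
- Bullet 2 also serves concomitant medications, which may well start before Day 0.

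All of this stands and limits the effect. It does not make the rule right for AEs: the safety tables count what falls inside the window, and the rule was written for records that remain incomplete after querying.

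A reader might also infer more than the documents support:

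- **That the error only removes events.** It does not. With the month missing, the rule also moves later 2019 onsets into Days 0-28.
- **That any missing month or year is exposed.** When the day is also missing, bullets 1 and 3 supply a floor, although the SAP does not say which bullet takes precedence.
- **That an event ending on Day 0 is moved to Day −1.** Bullet 5 specifies no shift; it simply conflicts with bullet 1.
- **That the tables labelled treatment-emergent are at risk.** In SAP 8.1 that label belongs to the solicited diary summary for Days 0-6. The exposed outputs are the unsolicited AE, MAE, SNMC and SAE summaries.
- **That one arm is favoured.** The rule is the same in both arms and site staff are blinded, so a bias between arms is unlikely.

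**Conclusion.** The defect is in the text of the SAP and does not depend on any assumption: bullet 2 lacks the Day 0 floor of bullets 1 and 3 and works against their stated purpose. Its size per affected record does depend on dosing in autumn 2019 and on equal weight for each onset day. On that footing, nearly half of early onsets with a missing month, and about half of all onsets with a missing year, would be dated before vaccination. The year-missing losses all come from Day 184 on, when only MAEs, SNMCs and SAEs are collected.

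These are shares of records with that missing pattern, not of all AEs. The effect on the reported percentages cannot be sized, because the documents give no count of partial dates. The conflict between bullets 1 and 5 is a separate, smaller fault. Both are worth correcting because the change is cheap and the outputs are primary safety summaries.

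**What to change.** For AEs, amend SAP 12.5 as follows:

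1. **Bullet 2:** impute the earliest date on or after Day 0 that agrees with the recorded parts and is not after the end date. Use a pre-vaccination date only if the recorded parts or the end date show that onset came first.
2. **Bullet 5:** let the imputed start be on or before the end date.
3. **Precedence:** state that bullets 1 and 3 govern when the day is also missing.
4. **Bullet 4:** apply the same Day 0 floor unless the end date is before Day 0.

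The cost is a few sentences and the matching program logic, with no new data and no extra analysis. With the year missing, the new rule returns the true date for every onset in Days 0-364. With the month missing, it leans further towards early onset: in the 21 October example, all of the 43 later 2019 onsets except those recorded on day 19 or 20 of the month (4 of them) would fall in Days 0-28, 39 instead of 26. That is the conservative direction that bullets 1 and 3 already choose, and the SAP should say it is intended.
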